Background	
The Cardioband Transcatheter System (Cardioband) is indicated for the treatment of secondary (functional) mitral regurgitation (FMR). The Cardioband is a transcatheter system, deployed on the beating heart through a transseptal approach. The Cardioband is deployed along the posterior annulus of the mitral valve and is adjusted under trans-esophageal guidance on the beating heart. 

Hypothesis	
 1) The Cardioband will reduce the severity of MR acutely with durable performance at 6 months 2) The Cardioband will improve 6 minute walk test at 6 months 3) The Cardioband will improve heart failure associated quality of life at 6 months
Objectives	
 1) To test the efficacy of the Cardioband in improving MR and heart failure symptoms in patients with symptomatic (NYHA Class III-IVa), severe MR in the post-marketing setting 2) To evaluate the safety of the Cardioband system in the post-marketing setting
Study design	
A multi-center (up to 20 sites) single arm open label study in n = 50 subjects. Subjects will be followed for up to 2 years.

Subject Population	
Patients with secondary (functional) MR, symptomatic (NYHA Class III-IVa heart failure symptoms), with severe MR and to whom The Local Site Heart Team concur that surgery will not be offered as a treatment option and that medical therapy is the intended therapy.

Endpoints	
Primary Endpoint (powered): Reduction in severity of MR at 30 days of at least one category on a 0-4 scale.
 
Key Secondary Endpoint (powered): Change in 6 minute walk test at 6 months.
 
Secondary Endpoints (all at 6, 12, and 24 months except as indicated) :
 
 1) MR severity 2) 6 minute walk distance 3) Quality of life as assessed by the Kansas City Cardiomyopathy Questionnaire (KCCQ) (also at 30 days) 4) NYHA Class (also at 30 days) 5) Left Ventricular End Diastolic Volume (LVEDV) 6) Left Ventricular End Systolic Volume (LVESV) 7) Device success defined as deployment of the Cardioband, with MR reduction at hospital discharge. 8) Individual patient success (6 months and 1 year) defined as device success and the following:

	REPAIR - Transcatheter REPAIR of Mitral Insufficiency with CaRdioband System Post Market Study Protocol ID CB1-3	
---	---	---

	
 • Discharged from index hospitalization • NYHA class improvement by at least 1 level from baseline 
9) Days alive and out of hospital (due to major cardiovascular events) at 1 year
 
10) Freedom from all-cause mortality and major adverse events defined as disabling stroke, myocardial infarction (peri-procedural or spontaneous), renal failure requiring dialysis, life-threatening bleeding, cardiac tamponade and device related cardiac surgical intervention at 30 days from the implant procedure or hospital discharge, whichever is later. (Individual components will also be evaluated).
 
11) Need for urgent/emergent surgical intervention

Sample Size Considerations	
Based on the results of the Cardioband CE mark study (Protocol ID CB 1-2), the present study with a sample size of 50 subjects will have greater than 80% power to detect a reduction in MR severity of at least one grade (CE mark study showed improvement in MR severity of at least one grade in >80% of subjects in CE mark study).
 
Based on the results of the Cardioband CE mark study (Protocol ID CB 1-2), the present study with a sample size of 50 subjects will have greater than 90% power to detect an improvement of 75 m in 6 minute walk test at 6 months (CE Mark study showed an improvement of 93.3 m ± 90.3 m).

Inclusion Criteria	
 1) Age ≥18 years 2) Severe (3+ to 4+) secondary Mitral Regurgitation 3) Symptomatic heart failure (NYHA Class III-IVa) despite guideline directed medical therapy including CRT if indicated 4) The Local Site Heart Team concur that surgery will not be offered as a treatment option and that medical therapy is the intended therapy. 5) Transfemoral access and transseptal deployment of the Cardioband is determined to be feasible 6) Subject is willing and able to provide informed consent and follow protocol
Exclusion Criteria	
 1) EF < 20% 2) LVEDD ≥ 70 mm 3) Heavily calcified annulus or leaflets 4) Significant CAD requiring revascularization 5) Active bacterial endocarditis 6) Any percutaneous coronary, carotid, endovascular intervention or carotid surgery within 30 days or any coronary or endovascular surgery within 3 months 7) Renal insufficiency requiring dialysis

	REPAIR - Transcatheter REPAIR of Mitral Insufficiency with CaRdioband System Post Market Study Protocol ID CB1-3	
---	---	---

	
 8) Life expectancy of less than twelve months 9) Subject is participating in concomitant research studies of investigational products that have not reached their primary endpoint 10) Pulmonary hypertension ≥ 70mmHg at rest 11) Mitral valve anatomy which may preclude proper device treatment 12) Right-sided congestive heart failure with echocardiographic evidence of severe right ventricular dysfunction and/or severe tricuspid regurgitation 13) Severe liver disease 14) Patient is pregnant or lactating 15) Hypersensitivity to Nickel or Chromium 16) Clinically significant bleeding diathesis or coagulopathy 17) History of mitral valve repair 18) TIA or CVA within 3 months 19) Subjects in whom transesophageal echocardiography is contraindicated 20) Patients who cannot tolerate anticoagulation/antiplatelet regimen 21) Patients with known severe reaction to contrast agents that cannot be adequately premedicated
Study Procedures	
Key Pre-Implantation Procedures:
 
 1. History and Physical 2. TTE , TEE and/or CT angiography 3. 6 minute walk test 4. KCCQ 
■ 
 
Key Post-Procedure Procedures:
 
 1. Serial AE assessment, history, and physical at 30 days, 6 months, 12 months, 24 months) 2. Serial TTEs (30 days, 6 months, 12 months, 24 months) 3. 6 minute walk tests (30 days, 6 months, 12 months, 24 months) 4. KCCQ (30 days, 6 months, 12 months, 24 months) 
■ 

	REPAIR - Transcatheter REPAIR of Mitral Insufficiency with CaRdioband System Post Market Study Protocol ID CB1-3	
---	---	---

ABBREVIATIONS

6MWT	6 minute walk test	ISO	International Standardization Organization
ADE	Adverse Device Effects	KCCQ	Kansas City Cardiomyopathy Questionnaire
AE	Adverse Event	LVEDD	Left Ventricle End-Diastolic Dimension
CABG	Coronary Artery Bypass Graft	LVEF	Left Ventricle Ejection Fraction
CDS	Cardioband Delivery System	MI	Myocardial infarction
CEC	Clinical Events Committee	MR	Mitral Regurgitation
CHF	Congestive Heart Failure	MSAE	Major Serious Adverse Event
COPD	Chronic obstructive pulmonary disease	NYHA	New York Heart Association
CRF	Case Report Form	QOL	Quality of Life
CRT	Cardiac Resynchronization Therapy	RO	Radiopaque
CT	Computerized Tomography	SADE	Serious Adverse Device Effect
CVA	CerebroVascular Accident	SAE	Serious Adverse Event
eCRF	Electronic Case Report forms	SAT	Size Adjustment Tool
EDC	Electronic Data Capture	SD	Standard Deviation
EF	Ejection Fraction	SOC	System Organ Class
FDA	Food and Drug Administration	SOP	Standard operating procedure
GC	Guide Catheter	TEE	Transesophageal Echocardiography
GCP	Good Clinical Practice	TF	Transfemoral
IC	Implant Catheter	TSS	Transseptal Steerable Sheath
ICD	Implantable Cardioverter-Defibrillator	TIA	Transient Ischemic Attack
IDS	Implant Delivery System	TTE	Transthoracic Echocardiography

	REPAIR - Transcatheter REPAIR of Mitral Insufficiency with CaRdioband System Post Market Study Protocol ID CB1-3	
---	---	---

TABLE OF CONTENTS

1. INTRODUCTION AND RATIONALE 9

2. DEVICE DESCRIPTION.....11

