3. STUDY DESIGN

3.1. Overview

The purpose of this PMS is to collect patient data related to mitral valve performance and safety outcomes in patients with severe functional mitral regurgitation (MR) in whom Cardioband will be implanted.

Subjects will be followed for up to 2 years,

A multi-center (up to 20 sites), single arm, open label study in a minimum of 50 subjects. Patients must have provided written consent that their data can be used in the study. The patients will be followed up for 2 years with the primary endpoint being at 6 months.

The study will enrol Patients with secondary (functional) MR, symptomatic (NYHA Class III-IVa heart failure symptoms), with severe MR and to whom The Local Site Heart Team concur that surgery will not be offered as a treatment option. Anatomical feasibility is assessed by Echocardiography and/or other exams (such as CT and angiography) according to the site common practice. The subjects will be screened and enrolled according to the study inclusion and exclusion criteria.

Patients will undergo mitral valve repair with Cardioband implanted via transcatheter procedure under Transesophageal echocardiography (TEE) and fluoroscopy guidance. Post-procedure clinical care will be performed according to standard management of mitral valve repair and Transthoracic Echo (TTE) assessment of the degree of mitral regurgitation will be obtained at hospital discharge, 30 days, 6, 12 and 24 months post-index procedure.

	REPAIR - Transcatheter REPAIR of Mitral Insufficiency with CaRdioband System Post Market Study Protocol ID CB1-3	
---	---	---

Transthoracic Echocardiography (TTE) performed by the Study clinical sites will be used for sequential assessments of mitral regurgitation at baseline, at discharge and during follow-up. Guidelines for recording the echocardiographic examination of mitral regurgitation will be provided to the sites. An echocardiographic Core Lab will be involved in assessing echocardiographic examinations. 

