3.2. Study Endpoints

3.2.1. Primary Endpoint (powered):

- Reduction in severity of MR at 30 days of at least one category on a 0-4 scale.

3.2.2. Key Secondary Endpoint (powered):

- Change in 6 minute walk test at 6 months

3.2.3. Secondary Endpoints (all at 6, 12, and 24 months except as indicated) :

- Key Secondary Endpoint (powered): Change in 6 minute walk test at 6 months.
- Secondary Endpoints (all at 6, 12, and 24 months except as indicated) :
 - 1) MR severity
 - 2) 6 minute walk distance
 - 3) Quality of life as assessed by the Kansas City Cardiomyopathy Questionnaire (KCCQ) (also at 30 days)
 - 4) NYHA Class (also at 30 days)
 - 5) Left Ventricular End Diastolic Volume (LVEDV)
 - 6) Left Ventricular End Systolic Volume (LVESV)
 - 7) Device success defined as deployment of the Cardioband, with MR reduction at hospital discharge.
 - 8) Individual patient success (6 months and 1 year) defined as device success and the following:
 - 9) Discharged from index hospitalization
 - 10) NYHA class improvement by at least 1 level from baseline
 - 11) Days alive and out of hospital (due to major cardiovascular events) at 1 year
 - 12) Freedom from all-cause mortality and major adverse events defined as disabling stroke, myocardial infarction (peri-procedural or spontaneous), renal failure requiring dialysis, life-threatening bleeding, cardiac tamponade, and device related cardiac surgical intervention

	REPAIR - Transcatheter REPAIR of Mitral Insufficiency with CaRdioband System Post Market Study Protocol ID CB1-3	
---	---	---

at 30 days from the implant procedure or hospital discharge, whichever is later. (Individual components will also be evaluated).

- 13) Need for urgent/emergent surgical intervention

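### Individual patient success at 6 months and 1 year takes its only MR component from hospital discharge, so a patient with recurrent MR or a second mitral intervention can still count as a success if NYHA class has improved

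*Combined protocol and SAP*

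**What the plan says.** In the synopsis, secondary endpoint 7 is "Device success defined as deployment of the Cardioband, with MR reduction at hospital discharge". Endpoint 8 is "Individual patient success (6 months and 1 year) defined as device success and the following", followed by two bullets: "Discharged from index hospitalization" and "NYHA class improvement by at least 1 level from baseline".

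Section 3.2.3 repeats these items but numbers the two bullets as endpoints in their own right. The second appears as "10) NYHA class improvement by at least 1 level from baseline". Item 8 there ends in a colon with no list under it, and no later MR component is added.

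Three other places bear on the point:

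- Hypothesis 1 in the synopsis reads "The Cardioband will reduce the severity of MR acutely with durable performance at 6 months".
- MR severity is secondary endpoint 1, under the heading "Secondary Endpoints (all at 6, 12, and 24 months except as indicated". Section 3.1 says that TTE "assessment of the degree of mitral regurgitation will be obtained at hospital discharge, 30 days, 6, 12 and 24 months post-index procedure", and Table 1 schedules it. Sections 3.1 and 5.1 provide for core-lab reading.
- Appendix 2 assesses device failure from 30 days onwards. Its 1-year patient-failure list includes device failure and repeat admission or intervention for the disease being treated. Its footnote calls an MR reduction acceptable when it is at least one grade and leaves residual MR at 2+ or less.

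**The concern.** An endpoint called patient success at 1 year after a mitral repair will be read as saying that the repair held and the patient felt better. As defined, it says that the repair worked at discharge and that NYHA class is better now. In a single-arm, open-label study, the only part measured at the named visit is a clinician-rated symptom class.

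This matters because the primary MR endpoint is at 30 days while Hypothesis 1 speaks of 6 months. A favourable 6- or 12-month success rate could be taken as support for durability that the endpoint does not measure. The same gap applies to reintervention. Section 6.3.4 allows referral for further structural heart treatment with continued follow-up, and nothing in endpoint 8 prevents an NYHA gain after a second mitral procedure from counting as success. That section provides for an extra subject if the treatment falls before the primary endpoint period is complete, but does not say that the treated patient leaves the analysis.

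**Working it through.** The plan gives no expected rate, target or power for this endpoint, so there is no figure to reproduce. The check is of the definition, followed by an illustration.

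**When each component is fixed**

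| Component | Fixed at | Can change by 6 or 12 months? |
|---|---|---|
| Device success (deployment and MR reduction) | Hospital discharge | No |
| Discharged from the index stay | Hospital discharge | No |
| NYHA better by one class or more | The visit | Yes |

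**Logical check.** Take a patient who is 4+ at baseline, 2+ at discharge, and back to 4+ on the 6-month TTE.

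- If NYHA has gone from III to II, all three conditions hold and the patient is a 6-month success.
- If NYHA is still III, the patient is not a success.

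Recurrence alone therefore never removes a patient from the success count, but it does not guarantee success either.

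**Illustration.** Inputs:

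- N = 50, the planned size, all treated as discharged and evaluable.
- D = 0.8148, the proportion with device success at discharge. Section 6.2.1 gives this figure for MR change at 30 days; using it for discharge is an assumption.
- r, the proportion of these whose MR reduction is lost by the visit: assumed.
- y = 0.70, the NYHA response without recurrence: assumed.
- y_r, the NYHA response with recurrence: assumed, from 0 to 0.70.

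Formulas:

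- As written: N × D × [(1 − r) × y + r × y_r]
- With MR reduction also required at the visit: N × D × (1 − r) × y
- Difference (recurred patients counted as successes): N × D × r × y_r

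N × D = 50 × 0.8148 = 40.74. At r = 20%:

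- With the visit criterion: 40.74 × 0.80 × 0.70 = 22.8.
- As written, y_r = 0: 22.8, difference 0.
- As written, y_r = 0.70: 40.74 × 0.70 = 28.5, difference 40.74 × 0.20 × 0.70 = 5.7, which is 5.7/50 = 11 percentage points.

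Recurred patients counted as successes, out of 50:

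| r | y_r = 0 | y_r = 0.25 | y_r = 0.50 | y_r = 0.70 |
|---|---|---|---|---|
| 10% | 0 | 1.0 | 2.0 | 2.9 |
| 20% | 0 | 2.0 | 4.1 | 5.7 |
| 30% | 0 | 3.1 | 6.1 | 8.6 |
| 50% | 0 | 5.1 | 10.2 | 14.3 |

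If NYHA response does not depend on recurrence (y_r = y), the count as written stays at 28.5 whatever the recurrence rate, even 100%.

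**The case against.** The case for leaving the endpoint alone has real force.

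- **The protocol does not assign Hypothesis 1 to this composite.** MR severity at 6, 12 and 24 months is its own endpoint, with scheduled TTEs and core-lab reading, and it can be cross-tabulated with NYHA from the same visits. This stands. A reader might infer that the trial cannot assess durability at all, and the documents do not support that. It remains true that MR severity is unpowered, has no durability criterion in the available text, and is not joined to symptoms within the patient.
- **NYHA improvement is still required.** This also stands. It would be wrong to say that every patient with recurrent MR is counted as a success.
- **Appendix 2 already provides later device-failure and patient-failure definitions.** It does, but endpoints 7 and 8 do not refer to them and use different timing. The appendix therefore shows a mismatch within the protocol and does not close the gap.
- **The heading of the secondary list could be read as moving device success to the later visits.** It allows exceptions, and endpoint 7 states its own time, hospital discharge.
- **The size rests on assumptions.** It does. No recurrence or NYHA-retention rate appears in the documents, and the lower end is zero.
- **This is one unpowered secondary endpoint with no test attached.** That limits the weight of the point, but the definition still decides who is reported as a success.

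**Conclusion.** The point holds as a flaw in the definition of one secondary composite. Its MR component is frozen at discharge, so at 6 months and 1 year it gives no direct information on whether the MR reduction lasted, and it does not exclude patients who needed another mitral intervention. It is also out of line with Appendix 2.

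Under the stated assumptions (81.48% device success at discharge, 20% recurrence, 0 to 70% NYHA response among recurred patients), the effect is 0 to 5.7 of 50 patients, or 0 to 11 percentage points. This is an illustration, not an estimate of bias. The primary endpoint, the key secondary endpoint, the sample size and the power are unaffected. It is a worthwhile, inexpensive improvement.

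**What to change.** In endpoint 8, in both the synopsis and 3.2.3:

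1. Keep the present components and add an MR reduction of one grade or more from baseline on the core-lab-read TTE of the same visit (6 and 12 months). This matches the threshold of the primary endpoint.
2. Count a patient who has had another mitral intervention by that visit as not successful.
3. Reconcile the definition with device failure and patient failure in Appendix 2. This includes stating whether residual MR must also be 2+ or less, since a fall from 4+ to 3+ meets a one-grade rule but not the appendix footnote.
4. State how a patient without a TTE at the visit is classified. This matters because 6.3.4 allows telephone follow-up after alternative treatment.
5. In 3.2.3, put items 9 and 10 back as components of item 8.

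Keep endpoint 7 unchanged as the acute measure.

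The cost is protocol wording and one missing-data rule. The TTEs are already scheduled, so no new assessments are needed. The reported success rate is likely to be somewhat lower.

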1. INTRODUCTION AND RATIONALE

Mitral regurgitation (MR) is a frequent disease associated with increased morbidity and mortality rates (1). Degenerative disease caused by damage to leaflets or other parts of the valve apparatus accounts for approximately one-third of the MR cases (DMR). The majority of patients suffer from functional mitral regurgitation (FMR) driven by adverse left ventricular remodeling due to ischemic or non-ischemic myocardial disease (2-4). Current guidelines are reluctant to advise isolated valve surgery of FMR since the prognostic benefit of surgical valve repair or replacement in typical high-risk heart failure patients is unclear (2, 5). Recent reports suggest that even patients in need for surgical coronary revascularization may not benefit from concomitant mitral valve surgery (6, 7). Therefore, surgical treatment of FMR is restricted to the small group of patients who require concomitant bypass surgery, or who are at considerably low risk for open-heart surgery with high-predicted surgical success rates. On the other hand, optimized medical therapy is ineffective in patients with significant FMR in order to control the progress of heart failure related morbidity and mortality (2, 5, 8-10). Consequently, reliable and predictable treatment for most patients with symptomatic FMR is lacking and there is an unmet need for alternative, catheter-based, minimal invasive interventional approaches. The edge-to-edge mitral valve repair with the MitraClip systems offers an effective and safe treatment option for non-surgical patients with either DMR or FMR (11). This direct approach on the mitral valve leaflets reduces MR severity and is associated with relief of heart failure related symptoms in up to 80% of treated patients (12). However, the MitraClip system has been developed for the treatment of DMR (13), and long-term outcome data on functional mitral valve disease are missing.

2. DEVICE DESCRIPTION

Cardioband	REPAIR - Transcatheter REPair of Mitral Insufficiency with CaRdioband System Post Market Study Protocol ID CB1-3	
-------------------	---	---

	REPAIR - Transcatheter REPAIR of Mitral Insufficiency with CaRdioband System Post Market Study Protocol ID CB1-3	
---	---	---

[figure not shown]
2.3 Indication/Contraindication

Cardioband Mitral Reconstruction System is indicated for the reconstruction and/or remodelling of pathological mitral valves.

[figure not shown]
The Cardioband logo is written in a stylized, cursive font.	
REPAIR - Transcatheter REPair of Mitral Insufficiency with CaRdioband System Post Market Study Protocol ID CB1-3
	A solid black rectangular box used for redaction.
---	---	---

[figure not shown]
Cardioband

REPAIR - Transcatheter REPAIR of Mitral Insufficiency
with Cardioband System
Post Market Study
Protocol ID CB1-3

	REPAIR - Transcatheter REPAIR of Mitral Insufficiency with Cardioband System Post Market Study Protocol ID CB1-3	
--	---	--

3. STUDY DESIGN

3.1. Overview

The purpose of this PMS is to collect patient data related to mitral valve performance and safety outcomes in patients with severe functional mitral regurgitation (MR) in whom Cardioband will be implanted.

Subjects will be followed for up to 2 years,

A multi-center (up to 20 sites), single arm, open label study in a minimum of 50 subjects. Patients must have provided written consent that their data can be used in the study. The patients will be followed up for 2 years with the primary endpoint being at 6 months.

The study will enrol Patients with secondary (functional) MR, symptomatic (NYHA Class III-IVa heart failure symptoms), with severe MR and to whom The Local Site Heart Team concur that surgery will not be offered as a treatment option. Anatomical feasibility is assessed by Echocardiography and/or other exams (such as CT and angiography) according to the site common practice. The subjects will be screened and enrolled according to the study inclusion and exclusion criteria.

Patients will undergo mitral valve repair with Cardioband implanted via transcatheter procedure under Transesophageal echocardiography (TEE) and fluoroscopy guidance. Post-procedure clinical care will be performed according to standard management of mitral valve repair and Transthoracic Echo (TTE) assessment of the degree of mitral regurgitation will be obtained at hospital discharge, 30 days, 6, 12 and 24 months post-index procedure.

	REPAIR - Transcatheter REPAIR of Mitral Insufficiency with CaRdioband System Post Market Study Protocol ID CB1-3	
---	---	---

Transthoracic Echocardiography (TTE) performed by the Study clinical sites will be used for sequential assessments of mitral regurgitation at baseline, at discharge and during follow-up. Guidelines for recording the echocardiographic examination of mitral regurgitation will be provided to the sites. An echocardiographic Core Lab will be involved in assessing echocardiographic examinations. 

